### **Study Purpose and Rationale**

The prevalence of obesity and associated metabolic diseases continues to rise yet effective non-surgical long-term treatments remain elusive. The success of dieting can be enhanced by pharmacological treatment. However considerable individual variability is observed in response to pharmacotherapy and there is no way to predict who will respond well to a given medication. Peripheral metabolic signals, including leptin and insulin, communicate levels of energy stores to key brain regions and elicit a host of neuronal responses that maintain energy balance; such regulatory mechanisms make it difficult to maintain diet-induced weight loss. The overall research objective is to characterize these mechanisms and to determine how they are impacted by pharmacotherapy in order to predict who will or will not respond to a given weight loss medication. Studies will focus on the melanocortin neuronal system, consisting of the proopiomelanocortin (POMC)-derived MSH peptides, the MSH antagonist, agouti related protein (AgRP) and brain melanocortin receptors, that plays a critical role in responding to these peripheral signals and maintaining energy balance (1). This protocol will focus on the weight loss drug lorcaserin (LOR) a serotonin (5HT2c) receptor agonist, as it works primarily by activation of POMC neurons and brain melanocortin signaling. POMC neurons express 5-HT2cR and are activated by 5-HT agonists (2) In addition, the obesity phenotype of the global 5-HT2cR KO mouse can be normalized by selective 5-HT2cR expression only in POMC neurons (3). Furthermore the feeding effects of 5-HT agonists are abolished by genetic inactivation of either Pomc or the Mc4-r (4,5). Effects on glucose homeostasis also require activation of the Mc4-r (6). Thus a functional brain melanocortin circuit is required for 5-HT agonists to exert their effects on both energy balance and glucose metabolism. LOR decreases body weight in humans primarily by suppressing food intake without affecting energy expenditure (7-10). A pooled analysis of two randomized trials of 4008 and 3182 patients demonstrated that 47% of drug treated subjects achieved at least 5% wt loss (vs 23% for placebo) while 22% of subjects achieved at least 10% wt loss (vs 9% for placebo) (11). There were also differences in body fat, lipids and glycemic indicators. As with other drug therapies, there was a lot of individual variability in response to treatment such that 53% did not achieve clinically significant wt loss. There is evidence that greater than 5% wt loss at 12 wks can be used to predict the response to LOR at 1 yr (12). However given that there are now many choices for drug therapy it would be helpful to be able to predict long-term efficacy based on a biochemical profile or the acute feeding response to the drug. We propose to quantitate the extent to which POMC neurons are activated by LOR as a predictor of acute changes in feeding and long-term wt loss. The ability of acute changes in feeding behavior to predict long-term wt loss will also be studied. This approach has been used by our collaborator, [name], to demonstrate that the response to a laboratory meal after one wk treatment with phentermine was predictive of subsequent wt loss after 6 months of treatment (13). In addition to documenting the activation of hypothalamic POMC neurons it is also important to understand other neural or neuroendocrine consequences of drug treatment that would serve to attenuate the therapeutic effects of LOR. This protocol will focus on changes in the hypothalamic-pituitary-adrenal (HPA) axis and AgRP that could limit the effectiveness of LOR treatment. Serotonin agonists have well documented stimulatory effects on the HPA axis (14-17) but until recently the underlying mechanism has not been well

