
defined (18). The 5-HT2C R is highly expressed in CRH neurons in the hypothalamus and mediates the activation of these neurons by serotonin agonists with subsequent stimulation of pituitary ACTH and adrenal corticosterone release (18). The effects of LOR treatment on the HPA axis have not been reported. Given the potent stimulatory effects of glucocorticoids on food intake it is important to determine if treatment with LOR has acute and chronic effects on the HPA axis and if these effects impact the efficacy of drug treatment (19). We have previously found that measurements of intact POMC prohormone in cerebrospinal fluid (CSF) can serve as a marker of central POMC activity in humans; plasma AgRP has also emerged as a potential biomarker for brain AgRP. There are striking correlations of CSF POMC with BMI, adiposity, leptin and insulin; strong correlations of plasma AgRP with these parameters are also found. Furthermore, following short-term diet-induced weight loss, levels of CSF POMC and the POMC-derived peptide,  $\beta$ -endorphin ( $\beta$ -EP), decrease while CSF and plasma AgRP levels increase. We will therefore study the acute (1 wk) effects of LOR vs placebo on these biomarkers and on feeding behavior, in response to a laboratory test meal, as predictors of the longer-term (24-wk) response to LOR. Counterregulatory mechanisms that may limit the effectiveness of LOR treatment will be assessed by measurement of AgRP in CSF and plasma and of HPA activity. HPA activity will be characterized using plasma, salivary, urine and CSF measurements. The validation of biochemical markers (CSF and plasma neuropeptides) and behavioral markers (feeding response) that are predictive of drug efficacy would facilitate the choice of drug when initiating therapy. Furthermore understanding the counterregulatory responses that develop in response to weight loss and drug therapy could lead to interventions that improve drug efficacy.

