### **Scientific Abstract**

The overall objectives of this study are to validate biomarkers that can be used to predict responses to the weight loss medication, lorcaserin, and to characterize counterregulatory responses to drug therapy that may limit efficacy. Studies will focus on the hypothalamic melanocortin (MC) system, including the proopiomelanocortin (POMC)-derived MSH peptides, the MSH antagonist, agouti related protein (AgRP) and brain MC-Rs, which are key mediators of the central response to weight loss. Lorcaserin is a serotonin (5HT2cR) agonist that works primarily by activation of POMC neurons and melanocortin signaling. We have found that measurements of the POMC prohormone in cerebrospinal fluid (CSF) can serve as a marker of central POMC activity in humans; plasma AgRP measurements have also emerged as a potential biomarker of brain AgRP activity. The current protocol will examine the acute (1 wk) effects of lorcaserin vs placebo on these biomarkers and on feeding behavior, in response to a laboratory test meal, as predictors of the longer-term (24-wk) response to lorcaserin. Counterregulatory mechanisms that may limit the effectiveness of lorcaserin treatment will also be characterized with a focus on the hypothalamic-pituitary-adrenal (HPA) axis and changes in AgRP levels. 60 healthy male and female subjects age 18-60 yr (BMI 28-42) will be recruited for a 5-wk double-blind crossover study with lorcaserin and placebo followed by treatment with lorcaserin or placebo for 24 wks. Participants will be randomized to receive either lorcaserin or placebo for 7 days followed by a 3 wk washout period and will then be crossed over to receive 7 days of the other treatment. On day 7 of both the placebo and lorcaserin treatments, subjects will be studied in the morning after an overnight fast in the clinical research center. A lumbar puncture (LP) will be performed to obtain CSF and blood samples will be obtained. Subjects will then be fed a standardized breakfast (300 kcal). A laboratory test meal will be performed 4h later. After completing the 7 day placebo and lorcaserin studies, subjects will then be continued on lorcaserin (n= 40) for 24 wks. Subjects will receive nutritional counseling to reduce their daily caloric intake to 600 kcal below their calculated caloric requirement and will be encouraged to exercise moderately for 30 min daily. Subjects will visit the clinic monthly during the 24 wk study period for counseling and to review food diaries; vital signs and safety labs will be monitored. Blood will be obtained for AgRP and hormone levels. At the end of the 24 wk period subjects will be admitted to the clinical research center for an LP followed by a

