### **Statistical Procedures**

40 subjects will be recruited to account for a predicted 20% dropout rate in order to retain 32 subjects. For phase 1, the primary outcome is difference in food intake after 7 days of drug compared to placebo. Based on known acute changes in food intake after LOR a sample size of 24 subjects would be required using paired analysis (10). This sample size is more than adequate if CSF POMC is used as the primary outcome variable using a SD of 59 fmol/m (for overweight and obese subjects) to detect a 20% change in CSF POMC as has been reported for hypothalamic POMC in animals after treatment with 5-HT2cR agonists (23). However in order to use the outcomes of phase 1 to predict phase 2 wt loss, 40 subjects will be recruited to retain 32 and to achieve a range of wt loss as predicted by clinical trials (9). Food intake, including food energy and macronutrient consumption will be correlated with baseline POMC and AgRP levels. Differences in food intake at the placebo and LOR test meals will be correlated with changes in melanocortin peptide levels as well as with wt loss after 24 wks. Multiple regression modeling will be used to predict phase 2 wt loss in the LOR-treated participants from the within-subject difference between LOR and placebo test meal results and CSF POMC measurements from Phase 1. Bivariate Pearson correlation coefficients will be determined and stepwise multiple regression analyses will be performed to detect associations between POMC and AgRP and changes in levels following LOR and placebo with relevant variables: wt change, food intake, adiposity, leptin, sOB-R, insulin, HOMA-IR, gut hormones. Phase 1 is a double-blind trial with lorcaserin and placebo. After 10 subjects completed phase 1 the investigators were unblinded to the treatment of those 10 subjects in order to perform an interim analysis on the neuropeptide changes. We did detect a significant change in CSF POMC levels in the first 10 subjects but changes were not significant for other POMC derived peptide values. We would now like to unblind the next 10 subjects who have completed phase 1 in order to perform an interim analysis on the first 20 subjects as this may help with determining if we need additional POMC-derived study markers and optimization of assay conditions. The double blind will then continue for the subsequent study subjects.

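### The model predicting Phase 2 weight loss has no baseline weight or BMI term, so CSF POMC, if entered as a level or a level-proportional change, could look predictive partly as a proxy for body size

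*Combined protocol and SAP*

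**What the plan says.** Under Statistical Procedures, the Phase 2 outcome is regressed on Phase 1 measurements: "Multiple regression modeling will be used to predict phase 2 wt loss in the LOR-treated participants". Two inputs are named, the lorcaserin-placebo contrast at the test meal and the Phase 1 values of CSF POMC. Weight, BMI and adiposity do not appear among these predictors. Nothing says whether weight loss is in kg, percent or BMI units; percent loss occurs only in background figures from other trials.

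The Study Purpose and Rationale reports: "There are striking correlations of CSF POMC with BMI, adiposity, leptin and insulin". That statement concerns CSF POMC itself, and no coefficient is given.

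The same section describes the intended predictor as a drug response, to "quantitate the extent to which POMC neurons are activated by LOR as a predictor of acute changes in feeding and long-term wt loss". The Scientific Abstract likewise plans to "examine the acute (1 wk) effects of lorcaserin vs placebo on these biomarkers and on feeding behavior".

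A separate set of Pearson correlations and stepwise regressions relates POMC and AgRP, both as levels and as changes, to "relevant variables: wt change, food intake, adiposity, leptin, sOB-R, insulin, HOMA-IR, gut hormones". Adiposity is a candidate variable there. It is not a fixed term in the prediction model.

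**The concern.** The plan itself links its key predictor to body size, then leaves body size out of the model that is meant to establish that predictor. If starting size also relates to weight loss, part of any POMC coefficient reflects size rather than response to the drug.

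The aim is to validate markers that help choose a drug before treatment starts. One of them requires a lumbar puncture, so it has to tell the clinician something that a scale does not. A model without baseline weight cannot answer that, even if the POMC term is significant.

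**Working it through.** **The plan's own figure.** "40 subjects will be recruited to account for a predicted 20% dropout rate in order to retain 32 subjects": 32/(1 − 0.20) = 40, which reproduces. No power, alpha or target correlation is stated for the Phase 2 regression. The check below uses 32 completers, all on lorcaserin in Phase 2, and two-sided 5%.

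**Inputs from the documents.** The rationale reports that 47% of treated patients lost at least 5% of weight and 22% lost at least 10% (time point not stated). Under normality:
- SD = (10 − 5)/(z(0.78) − z(0.53)) = 5/(0.772 − 0.075) = 7.2%
- mean = 5 − 0.075 × 7.2 = 4.5%

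**Assumed inputs, not in the documents.** POMC-weight correlation 0.5-0.7; weight coefficient of variation (CV) 12-18%; correlation of percent loss with weight 0, or 0.2-0.3. POMC has no effect of its own.

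**Mechanism.** If POMC relates to loss only through body size, the induced correlation is r(POMC, size) × r(loss, size). With 32 subjects and two predictors, the chance of a significant POMC term is approximately Φ(√28·atanh r − 1.96) + Φ(−√28·atanh r − 1.96).
- 0.5 × 0.2 = 0.10: √28 × 0.100 = 0.53, giving about 8%.
- 0.5 × 0.3 = 0.15: √28 × 0.151 = 0.80, giving about 13% (simulated 12%).
- 0.7 × 0.3 = 0.21: √28 × 0.213 = 1.13, giving about 20% (simulated 21%).

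**Does the kg scale create the problem by itself?** If percent loss is unrelated to weight, then r(kg loss, weight) = mean × CV / √[(mean × CV)² + SD²(1 + CV²)]. At a CV of 15% this is 0.67/√(0.45 + 52.6) = 0.09. Multiplied by 0.5-0.7, it leaves a correlation of only about 0.05-0.06 between POMC and kg lost.

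**Simulated false-positive rate for POMC entered as a level** (n = 32, 20,000 runs per scenario):

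| Percent loss vs weight | Outcome | No weight term | Weight term added |
|---|---|---|---|
| r = 0 | kg | about 6-7% | about 5% |
| r = 0 | percent | about 5% | about 5% |
| r = 0.2-0.3 | kg | about 11-32% | about 5% |
| r = 0.2-0.3 | percent | about 8-21% | about 5% |

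**POMC entered as the lorcaserin-placebo change.** This run used BMI as the size measure and no BMI term, with assumed correlations of 0.3-0.7 (POMC with BMI) and 0.3-0.5 (loss with BMI).
- Additive drug effect: about 5%, because a stable body-size component cancels in the difference.
- Effect proportional to baseline (a 20% rise, with mean POMC of 200 and noise SD of 15-30 assumed, and the plan's SD of 59): 5-22%.

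**Cost of the extra term.** The partial correlation detectable with 80% power is tanh[(1.96 + 0.84)/√28] = 0.485 with two predictors and tanh[(1.96 + 0.84)/√27] = 0.492 with three.

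**The case against.** The strongest reply is that the predictor is a change, not a level. In "the within-subject difference between LOR and placebo test meal results and CSF POMC measurements from Phase 1" the within-subject difference can govern both nouns, and the rationale and abstract both speak of the acute drug effect. The reported BMI correlations concern CSF POMC itself; nothing says that its lorcaserin-placebo change tracks BMI. This largely stands: with an additive change the false-positive problem disappears. It does not close the point, for three reasons. The sentence can equally be read as POMC levels. The sample-size text frames the POMC effect as a percentage change, under which some of the dependence on level returns. And the separate correlations relate POMC levels to weight change on any reading, with stepwise selection giving no assurance that adiposity stays in.

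Second, no passage links body size to weight loss. That is correct, and it is why the rates above are conditional.

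Third, the aim is prediction, so a predictor that works through BMI is not strictly false. That is fair for association, but not for a claim that POMC is a useful marker of drug response.

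A reader might go further and infer that loss in kg scales with starting weight strongly enough to create the artefact by itself. The documents' responder figures do not bear this out: the rate rises only to about 6-7%. A reader who assumed a mean loss of 6% with an SD of 4-5% could obtain 14-53% under the weak link, but those inputs are narrower than the spread implied by the plan's own background figures.

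**Conclusion.** The point holds conditionally. It is established that the prediction model names no body-size term, that the plan reports strong POMC-BMI correlations, and that neither the form of POMC nor the weight-loss scale is fixed. It is not established that POMC will act as a proxy. That requires POMC to enter as a level, or as a change proportional to level, and body size to be related to weight loss.

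Under those conditions and the stated assumptions, the nominal 5% error rate becomes roughly 8-32%, depending on scale and correlations. Outside them it stays near 5-7%. The correlations and weight CV are assumptions, and the mean and SD of loss rest on normality and on other trials' responder rates.

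Independently of these rates, the model as written cannot show that CSF POMC adds to baseline weight. That alone justifies the change, given how little it costs.

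**What to change.** 1. Force baseline weight or BMI, measured at the start of Phase 2, into the Phase 2 prediction model, outside any stepwise selection.
2. Report the gain in R-squared from the POMC term and the test-meal difference over a model with baseline weight (or BMI) alone.
3. Define the outcome as percent change from weight at the start of Phase 2. This complements the covariate and does not replace it, since percent loss without the covariate still gave 8-21% under a weak link.
4. State that POMC enters as the lorcaserin-placebo change, as the rationale and abstract describe, and adjust any analysis of POMC level for baseline weight or BMI as well.

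The cost is wording in Statistical Procedures and one degree of freedom, with the detectable partial correlation moving from about 0.485 to 0.492. BMI is already an eligibility measure, and a starting weight is needed anyway to calculate Phase 2 loss.

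### Stepwise regression is planned for the POMC and AgRP associations, and the separate weight-loss prediction model has no validation step, although the stated aim is to validate predictors

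*Combined protocol and SAP*

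**What the plan says.** The Scientific Abstract sets the goal: "The overall objectives of this study are to validate biomarkers that can be used to predict responses to the weight loss medication". It closes by returning to validation of both biochemical and feeding markers.

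Statistical Procedures contains two different analyses that bear on this.

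- **Association screen.** Alongside bivariate Pearson correlations, "stepwise multiple regression analyses will be performed to detect associations between POMC and AgRP and changes in levels following LOR and placebo". The other side of these associations is a list of "relevant variables: wt change, food intake, adiposity, leptin, sOB-R, insulin, HOMA-IR, gut hormones". No entry or removal rule, model direction, multiplicity rule or exploratory label is given.
- **Weight-loss model.** "Multiple regression modeling will be used to predict phase 2 wt loss in the LOR-treated participants", using the within-subject test-meal difference between lorcaserin and placebo and the phase 1 CSF POMC measurements. It is not called stepwise. No cross-validation, bootstrap, hold-out sample or external cohort is described.

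On numbers, "40 subjects will be recruited to account for a predicted 20% dropout rate in order to retain 32 subjects". On the primary outcome, "For phase 1, the primary outcome is difference in food intake after 7 days of drug compared to placebo". On interim looks, "We did detect a significant change in CSF POMC levels in the first 10 subjects", and a second unblinded look at the first 20 is requested, partly to decide whether further POMC-derived markers are needed.

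**The concern.** Stepwise selection chooses variables because they look strong in the sample at hand, then reports p-values and R-squared as if they had been chosen beforehand. Both come out too favourable even when the procedure is followed exactly.

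Validation means showing that performance holds beyond the data used for fitting. Nothing in Statistical Procedures does that for the weight-loss model. The feeding marker has earlier support, since the rationale reports that "the response to a laboratory meal after one wk treatment with phentermine was predictive of subsequent wt loss after 6 months of treatment". But that was another drug, and no fitted equation is carried forward to be tested here. This sample can therefore develop a model and, at most, validate it internally.

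One choice in the weight-loss model is also open: food intake is said to include both energy and macronutrients, and the plan does not fix which test-meal result enters.

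At stake is whether associations from the screen are real, and whether the reported R-squared describes how well phase 1 measures would predict response in new patients.

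**Working it through.** **Sample size.** Inputs from Statistical Procedures: 32 retained, 20% dropout. 32 / (1 − 0.20) = 40, so the plan's figure reproduces. (The Scientific Abstract gives 60 subjects; the figures here use 40 and 32.) I take n = 32 for analyses needing 24-week data, and n = 40 as the upper limit for phase 1 associations.

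**Stepwise screen where nothing is associated.** Assumptions not in the documents: entry at two-sided p < 0.05, a peptide as outcome, and the eight items as eight candidates.

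- Uncorrelated candidates: P(at least one kept) ≈ 1 − 0.95^8 = 0.34.
- Simulated forward selection, n = 32: 0.336 uncorrelated, 0.262 at correlation 0.5, 0.187 at correlation 0.7. A second simulation with a removal rule (p > 0.10) gave 0.346 uncorrelated. The range is about 19% to 35%.
- At n = 40: 0.332, 0.257 and 0.191.
- Smallest R-squared that a first variable can show: critical |r| at n = 32 is 0.349, and 0.349² = 0.12. When something is kept, the simulated mean apparent R-squared is 0.21 to 0.22, and R-squared in new data is −0.27 to −0.29.

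**Weight-loss model.** Assumptions: two fixed uncorrelated predictors, n = 32, normal data. Simulated means (1500 replicates, 100 bootstraps each):

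| True R² | Apparent | Adjusted | Bootstrap-corrected | Leave-one-out | New patients |
|---|---|---|---|---|---|
| 0 | 0.066 | 0.002 | −0.089 | −0.073 | −0.107 |
| 0.1 | 0.155 | 0.097 | 0.019 | 0.030 | 0.006 |
| 0.2 | 0.239 | 0.187 | 0.120 | 0.126 | 0.116 |
| 0.3 | 0.327 | 0.280 | 0.224 | 0.227 | 0.225 |

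Checks by formula:

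- Null apparent R² = p/(n − 1) = 2/31 = 0.065.
- Adjusted R² = 1 − (1 − 0.239) × 31/29 = 0.187.
- New-patient R² = 1 − (1 − true R²) × (n + 1)(n − 2) / [n(n − p − 2)] = 1 − 0.80 × (33 × 30)/(32 × 28) = 1 − 0.80 × 1.105 = 0.116.

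The overall F-test rejects in 5.1% of null trials, so it is not inflated. At true R² 0.20 the SD across trials is 0.152 for the bootstrap-corrected value and 0.147 for leave-one-out.

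The leave-one-out figures use the left-out mean in the denominator. With the full-sample mean, the denominator shrinks by (31/32)² and 0.126 becomes 1 − 0.874 × (32/31)² = 0.07, so the convention must be named.

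**Cost of multiplicity control.** Detectable |r| at 80% power, n = 32, is tanh[(z for two-sided α + 0.842)/√29]. Unadjusted: tanh(2.802/5.385) = 0.48. Bonferroni over 8 tests: 0.58; over 16: 0.61.

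**The case against.** The strongest reply is that the two analyses should not be run together, and that the one serving the objective is in reasonable shape. Its F-test is sound. Adjusted R-squared (0.19) nearly recovers the true 0.20. The 0.12 answers a different question, namely how the fitted equation would perform in new patients, and nobody proposes to deploy an equation. A corrected R-squared averaging 0.12 with an SD of about 0.15 can hardly be told from zero in one trial. Much of this stands, and it is why the optimism is called modest. It does not meet the stated aim: a claim to have validated predictors needs evidence beyond the apparent fit, and a wide interval is itself an honest result.

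For the screen, the null figures apply only to unassociated pairs, and Study Purpose and Rationale reports real correlations of CSF POMC with adiposity, leptin and insulin. That limit stands. The lack of a multiplicity rule also rests on silence in the plan.

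A reader might infer more than the documents support:

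- **That weight loss is predicted by stepwise selection.** The word is attached only to the POMC and AgRP screen. Weight change is on that list, but the prediction model is described separately.
- **That the interim looks bias the weight-loss model.** The looks described concern neuropeptide changes in phase 1, not their relation to weight loss. A mean drug effect on POMC does not bias a regression of weight loss on POMC. Only markers added afterwards raise an issue.
- **That the choice between POMC level and POMC change is wide open.** Study Purpose and Rationale proposes the extent of POMC activation by the drug as the predictor, which points to change.
- **That false findings would exceed half of analyses.** This needs about 16 uncorrelated candidates in one model. The plan names eight items, several plainly correlated, such as insulin with HOMA-IR.

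**Conclusion.** The point holds in two separate parts. First, the stepwise screen is a method that biases p-values and R-squared as specified. Where nothing is associated, it keeps something in about 19% to 35% of analyses with 8 candidates at n = 32. That rests on an assumed entry rule, candidate count, model direction and correlation between candidates (0.7 down to none). Second, the weight-loss model lacks any validation step and leaves its test-meal measure open. Its optimism is modest but real: 0.24 apparent against 0.12 in new patients, assuming two fixed predictors and a true R-squared of 0.20. The phase 1 primary comparison of food intake is not affected. This should be changed, but it does not threaten the trial's primary result.

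**What to change.** - Make the weight-loss model the main prediction analysis. Force in the lorcaserin-minus-placebo test-meal energy difference and the lorcaserin-minus-placebo CSF POMC difference, with no selection.
- Beside its apparent R-squared, report the adjusted value and a bootstrap optimism-corrected value with a confidence interval. Leave-one-out with the left-out mean in the denominator is an acceptable alternative.
- Replace the stepwise search with models listed in advance, or with a penalised model whose cross-validation repeats all selection and tuning. Label these models and the correlations exploratory.
- Label any marker added after an interim look as added later.
- Describe the aim as developing and internally validating predictors unless an independent sample is used.

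The cost is wording and a little more analysis, with no new data. The reported R-squared will be smaller and its interval visibly wide. Multiplicity control of the exploratory correlations is optional, because raising the detectable |r| from 0.48 to 0.58 or more is a real loss of sensitivity at this sample size.

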## Study Design

40 healthy male and female subjects age 18-60 yr will be recruited for this study (BMI 28-40). Exclusion criteria include any clinically significant medical condition, including diabetes, uncontrolled hypertension, heart disease, bleeding disorder, kidney or liver dysfunction, neurologic disease, psychiatric or eating disorders; use of tobacco or opiates or history of alcohol or drug abuse; recent weight change  $\pm 5\%$ ; or medications that affect body weight. Subjects will have a physical examination and screening blood studies, including fasting glucose levels, comprehensive metabolic panel and CBC. An EKG will also be performed.

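### Men and women are pooled, with no sex term, in the between-subject POMC and AgRP correlations and regressions; add sex-adjusted estimates

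*Combined protocol and SAP*

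**What the plan says.** Study Design states that "40 healthy male and female subjects age 18-60 yr will be recruited for this study". It gives no sex ratio or quota and no stratification by sex.

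Statistical Procedures is the whole analysis plan. It says "Bivariate Pearson correlation coefficients will be determined and stepwise multiple regression analyses will be performed" to relate POMC, AgRP and their changes "with relevant variables: wt change, food intake, adiposity, leptin, sOB-R, insulin, HOMA-IR, gut hormones". It also correlates food intake with baseline peptide levels, and the drug-placebo difference in intake with peptide changes and with 24-week weight loss. Finally, "Multiple regression modeling will be used to predict phase 2 wt loss in the LOR-treated participants", using the within-subject test-meal difference and Phase 1 CSF POMC as predictors.

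Sex appears in none of these analyses, and no analysis by sex is described. Study Purpose and Rationale reports that "There are striking correlations of CSF POMC with BMI, adiposity, leptin and insulin", without coefficients and without separating men from women.

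**The concern.** When two variables both differ between two groups, they correlate in the pooled sample even if they are unrelated within each group. When only one differs, or the two differ in opposite directions, a real within-group relation is weakened in the pooled sample. Correlations of one level with another, such as baseline POMC against food intake, leptin or adiposity, are fully open to this. A bivariate Pearson coefficient adjusts for nothing, and stepwise selection cannot pick a variable that is not a candidate.

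The study aims to validate biomarkers, some of them obtained by lumbar puncture. A sex difference could be reported as a melanocortin mechanism, or a real relation could be missed. A CSF marker that only restates sex would add nothing to prediction.

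**Working it through.** **Inputs from the plan.** "40 subjects will be recruited to account for a predicted 20% dropout rate in order to retain 32 subjects". This reproduces: 32 / (1 - 0.20) = 40. The check uses n = 32; correlations that need only Phase 1 data could have a few more subjects. (The Scientific Abstract gives 60 subjects, which is a separate inconsistency.)

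**Assumed inputs, because the documents give none.** These are the standardized sex gaps d1 and d2 in the two variables (in within-sex SDs), the share p of one sex, and the within-sex correlation r_w. Tests are two-sided at 0.05.

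**Formula.** With q = p(1 - p):

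pooled r = [r_w + q·d1·d2] / √[(1 + q·d1²)(1 + q·d2²)]

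Example with p = 0.5, d1 = d2 = 1 and r_w = 0: 0.25 / 1.25 = 0.20. With both gaps 1.5: 0.5625 / 1.5625 = 0.36.

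The rejection rates below come from at least 20,000 simulated data sets per scenario at n = 32.

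**No within-sex relation (r_w = 0): false-positive rate**

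| Gaps (SD) | Pooled r, p = 0.5 | Rate, p = 0.5 | Rate, p = 0.75 |
|---|---|---|---|
| 1.5 and 0 | 0.00 | 5% | 5% |
| 0.5 and 0.5 | 0.06 | 6% | 6% |
| 1 and 0.3 | 0.07 | 6% | 6% |
| 1 and 0.5 | 0.11 | 9% | 7% |
| 1 and 1 | 0.20 | 20% | 14% |
| 1.5 and 1 | 0.27 | 33% | 23% |
| 1.5 and 1.5 | 0.36 | 57% | 40% |

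The sex-adjusted partial correlation stays at about 5% in every row.

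The rows with 0.3 and 0.5 matter because of how a POMC gap might arise. If POMC differs by sex only because it tracks leptin or adiposity, its gap is the within-sex correlation times the leptin gap. An assumed correlation of 0.3-0.5 and a leptin gap of 1 SD give 0.3-0.5 SD.

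**True within-sex r_w = 0.5: power**

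| Gaps (SD) | Pooled r, p = 0.5 | Pooled power, p = 0.5 | Pooled power, p = 0.75 | Adjusted power |
|---|---|---|---|---|
| 0 and 0 | 0.50 | 85% | 85% | 84% |
| 1 and 0 | 0.45 | 75% | 77% | 84% |
| 1.5 and 0 | 0.40 | 63% | 68% | 84% |
| 1 and -0.5 | 0.33 | 44% | 54% | 84% |
| 1 and -1 | 0.20 | 16% | 28% | 84% |

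Example for 1.5 and 0: 0.5 / √1.5625 = 0.40.

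**Cost of one sex term.** The critical |r| is t / √(df + t²). With 30 df it is 2.042 / √(30 + 4.171) = 0.349; with 29 df it is 2.045 / √(29 + 4.183) = 0.355. The r detectable with 80% power is tanh(2.802 / √29) = 0.478 without the term and tanh(2.802 / √28) = 0.485 with it.

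**Which analyses are exposed.** The level-on-level correlations are fully exposed. A within-subject drug-placebo difference removes any constant sex difference in level, though not one that grows with intake. The Phase 1 primary outcome compares each subject with himself or herself.

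**The case against.** The strongest objection is that the premise is not in the documents. No section gives a sex difference in leptin, adiposity, intake, POMC or AgRP, or the expected sex split. A false association needs the peptide itself to differ by sex; if it does not, the rate stays at 5%. If POMC differs only through leptin or adiposity, the rate is 6-9% with a 1 SD gap in the other variable. This stands, and it means the 20% and 57% figures are scenarios, not expected error rates. It does not answer the loss of power, which needs a gap in only one variable.

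Second, adiposity is among the listed variables and may carry part of a sex difference. That protection is partial: stepwise selection may drop adiposity, and the bivariate correlations do not have it. The list also names variables to be related to the peptides and is not a set of covariates. The supportable statement is therefore that no sex adjustment is specified.

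Third, the pooled correlation is a legitimate quantity for a marker meant for a mixed population. This also stands, and it is a reason to report both estimates. Age (18-60) is unlisted too, which does not remove the case for sex.

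A reader might infer that every peptide analysis, or even the primary result, is confounded by sex. The documents do not support that. The primary comparison is paired and is not biased by a sex difference in intake. For the intake difference against weight loss, a constant sex gap cancels on the intake side. The plan also attaches no confirmatory decision rule to the correlations.

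**Conclusion.** The omission is real, and it matters mainly for correlations and regressions of peptide levels on food intake, leptin, adiposity and related levels. How much it matters is unknown. It ranges from negligible (about 6% false positives at 0.5 SD gaps) to serious (57% at 1.5 SD in both), and is lower when one sex predominates. The loss of power, from about 84% to 75% or 63% at a within-sex r of 0.5, needs the weaker assumption. The weight-loss model is exposed through its POMC level term only if weight loss also relates to sex, for which the documents give no figure. These results assume n = 32, normal data with equal within-sex variances, and the stated gaps. The recommendation rests less on any one scenario than on the low cost of adjusting.

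**What to change.** In Statistical Procedures:

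- Add sex-adjusted partial correlations beside the pooled Pearson correlations, and report both.
- Force sex as a fixed term in the stepwise regressions and in the weight-loss model, so that selection cannot remove it.
- Base any claim of a melanocortin association, or of added predictive value, on the sex-adjusted estimate.
- Mark scatterplots by sex.
- Record that this rule was added after ten subjects had been unblinded for the interim neuropeptide analysis, and state whether the proposed second unblinding had taken place by then.

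The cost is one degree of freedom (power at r = 0.5 goes from about 85% to 84% when there is no sex difference) and a dated amendment. No new data, visits or subjects are needed, since the sex of each subject is known.
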